5. TREATMENT PLAN

5.1 Treatment Regimen

The rationale for selection of doses to be used in this trial is provided in Section 2.3 – Rationale.

Details on preparation and administration of pembrolizumab are provided in the Pharmacy Manual.

Pembrolizumab will be administered once every 3 weeks, with 21 consecutive days defined as a treatment cycle (unless the treatment cycle length is increased for adverse effect, as detailed in Section 6). Treatment will be administered on an outpatient basis. Reported adverse events and

potential risks are described in Section 7. No dose reductions are allowed. No investigational or commercial agents or therapies other than those described below may be administered with the intent to treat the participant's malignancy.

All participants will receive pembrolizumab at a fixed dose of 200 mg intravenously every 3 weeks for up to 35 cycles (approximately 2 years) or until disease progression, prohibitive toxicity, withdrawal of consent, or investigator discretion.

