5.6 Duration of Follow Up

Participants will be followed for survival every 12 weeks (\pm 14 days) for 24 months after completion of protocol therapy, discontinuation of protocol therapy or until death, whichever occurs first. Survival follow-up may be conducted by telephone or email contact with the participant or his/her primary physician. Participants removed from protocol therapy for unacceptable adverse event(s) will be followed until resolution or stabilization of the adverse event regardless of the duration of follow-up required.

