5.7 Criteria for Taking a Participant Off Study

Participants will be removed from study when any of the following criteria apply:

- Completion of all study-related activities
- Lost to follow-up
- Withdrawal of consent
- Death

The reason for taking a participant off study, and the date the participant was removed, must be documented in the case report form (CRF).

For Centralized Subject Registrations, the research team submits a completed Off Treatment/Off Study form to ODQ when a participant comes off study. This form can be found on the ODQ website or obtained from the ODQ registration staff.

For Decentralized Subject Registrations, the research team updates the relevant Off Treatment/Off Study information in OnCore.

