6. DOSING DELAYS/DOSE MODIFICATIONS

There will be no dose modifications on this study. Dose delays will be made as indicated in the following table(s). The descriptions and grading scales found in the revised NCI Common Terminology Criteria for Adverse Events (CTCAE) version 4.0 will be utilized for dose delays and dose modifications. A copy of the CTCAE version 4.0 can be downloaded from the CTEP website:

http://ctep.cancer.gov/protocolDevelopment/electronic_applications/ctc.htm

If a participant is delayed but is subsequently able to resume treatment, then subsequent visits, assessments and treatments will continue every 3 weeks (unless the dosing interval is modified per Table 2) **from the time treatment has resumed until all cycles of therapy are completed.** For example, if cycle 4 is delayed 2 weeks and administered on week 12 instead of 10, cycle 5 and its corresponding assessments should take place on week 15, cycle 6 on week 18, etc.

Pembrolizumab will be withheld for drug-related Grade 4 hematologic toxicities, non-hematological toxicity \geq Grade 2 or 3 (depending on nature of toxicity) including laboratory abnormalities, and severe or life-threatening AEs as per Tables 2 and 3 below. If there is a question as to whether an AE is or is not immune-related, this should be discussed with the study chair.

Table 2. Dose Modification Guidelines for Hematological Drug-Related Adverse Events.

Toxicity	Grade	Hold treatment	Timing for restarting treatment	Treatment discontinuation
Hematological	1,2,3	No	N/a	N/a
	4	Yes	Toxicity resolves to grade ≤ 1	Toxicity does not resolve within 12 weeks of last infusion Permanent discontinuation should be considered for any life-threatening event

Adverse events (both non-serious and serious) associated with pembrolizumab exposure may represent an immunologic etiology. These adverse events may occur shortly after the first dose or several months after the last dose of treatment. Pembrolizumab must be withheld for drug-related toxicities and severe or life-threatening AEs as per Table 3 below.

Table 3. Dose modification guidelines for non-hematological drug related adverse events including immune related adverse events (irAEs)

General instructions:				
Immune-related AEs	Toxicity grade or conditions (CTCAEv4.0)	Action taken to pembrolizumab	irAE management with corticosteroid and/or other therapies	Monitor and follow-up

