13.2 Sample Size, Accrual Rate and Study Duration

13.2.1 Sample size

The study will be powered based on the number of patients with EBV+ DLBCL enrolled. Patients with other allowed lymphoma histologies will be enrolled until the accrual goal of 20 patients with EBV+ DLBCL/TCHRLCL/plasmablastic lymphoma is met (with a maximum of 10 patients in any given lymphoma histology) at which time accrual to all lymphoma cohorts will close. The exact number of patients enrolled depends on the accrual of non-EBV+ DLBCL patients, but is expected to be 24-30 patients. If by the time 20 patients with EBV+ DLBCL are accrued, the total accrual is <24, accrual will continue to all 3 cohorts (including EBV+ DLBCL) until the total accrual reaches 24.

Six patients with histiocytic sarcoma, follicular dendritic cell sarcoma, and/or interdigitating dendritic cell sarcoma will be included in the trial and accrual to this subgroup can continue independent of closure of the study to accrual of lymphoma patients. Given the extremely rare

nature of these diseases, these patients are being included for exploratory purposes only and the statistics of the trial will not be powered based upon this patient population.

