13.2.2 Statistical considerations

The hypothesis of this trial is that the response rate of pembrolizumab in this patient population will be 40% or higher. Assuming at least 20 patients are enrolled, we would consider the treatment promising if at least 6 patients respond. With this design, the study would have approximately 87% power to detect a difference in the response rate between 15% (the null hypothesis) and 40% (the alternative hypothesis), at a significance level of 0.07 (based on the exact binomial distribution). The maximal 90% confidence interval around the estimates for response and toxicity will be approximately +/-20%.

We anticipate accrual of 1 patient per month yielding an accrual period of 24 months. We anticipate following the last patient accrued for 6 months before being able to determine best overall response (the primary endpoint). Patients will be followed for 2 years after accrual for secondary endpoints such as PFS, OS, and duration of response for total study duration of approximately 4 years.

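### Do the 24-month accrual period and four-year duration in Section 13.2.2 need changing because they fit only 24 patients and a different follow-up clock from Section 5.6?

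*Combined protocol and SAP*

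**What the plan says.** Section 13.2.2 gives the timeline: "We anticipate accrual of 1 patient per month yielding an accrual period of 24 months". Best overall response is to be determined once the last patient has been followed for six months. For the later endpoints, "Patients will be followed for 2 years after accrual for secondary endpoints such as PFS, OS, and duration of response", giving a total of about four years.

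Section 13.2.1 says the number enrolled is "expected to be 24-30 patients", with 24 as the minimum total. A separate paragraph adds six patients with histiocytic or dendritic cell sarcomas, for exploration only, and says that "accrual to this subgroup can continue independent of closure of the study to accrual of lymphoma patients".

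Section 5.6 has survival contacts every 12 weeks "for 24 months after completion of protocol therapy, discontinuation of protocol therapy or until death, whichever occurs first". Section 5.1 allows up to 35 three-week cycles, and Section 6 lets the schedule continue after a delay "from the time treatment has resumed until all cycles of therapy are completed". The off-study list in Section 5.7 opens with "Participants will be removed from study when any of the following criteria apply" and names completion of study activities, loss to follow-up, withdrawal and death. Section 14 places the end of the study either at the last data items or at data maturity, and for the latter refers back to Section 13.2.

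**The concern.** A reader who checks Section 13.2.2 against its neighbours finds three loose ends. The 24-month accrual period works only at the bottom of the expected enrolment range. The two-year follow-up starts at accrual in one place and at the end of therapy in another, and therapy can itself last about two years. The end of the study is given as two alternatives, one of which leads back to the four-year figure. Footnote d of the Study Calendar makes the end of study one of the points at which imaging stops for patients off treatment without progression.

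If about four years were enforced as a closing date, late enrolees would lose some of the survival contacts planned in Section 5.6, and some off-treatment scans would stop early. Progression-free survival, overall survival and duration of response would then be less mature than the plan suggests. The month at which the primary endpoint can be read would also be later than forecast if 30 patients were enrolled.

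**Working it through.** **Inputs.** Accrual rate: 1 per month (13.2.2). Enrolment N: 24 to 30 (13.2.1). Follow-up: 24 months after accrual (13.2.2) or 24 months after therapy ends (5.6). Longest undelayed therapy: 35 cycles of 21 days (5.1). Mean month: 365.25/12 = 30.4375 days.

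**1. The plan's own figures.** Accrual = N / rate = 24/1 = 24 months. Total = 24 + 24 = 48 months = 4.0 years. Both stated figures reproduce.

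**2. Top of the expected range, same clock.** Accrual = 30/1 = 30 months. Total = 30 + 24 = 54 months = 4.5 years. Enrolling 30 patients in 24 months would need 30/24 = 1.25 per month.

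**3. The six sarcoma patients.** Their separate paragraph and separate closure point to their being additional to the 24 to 30. The plan does not say whether the rate of 1 per month covers them, so I calculate no total for them.

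**4. The Section 5.6 clock for the last enrolee.**
- Full therapy: 35 × 21 = 735 days; 735/30.4375 = 24.1 months. Total = 24 + 24.1 + 24 = 72.1 months for N = 24, and 30 + 24.1 + 24 = 78.1 months for N = 30.
- One cycle only: 21/30.4375 = 0.7 months. Total for N = 24 = 24 + 0.7 + 24 = 48.7 months.

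For the last enrolee the gap between the clocks equals the time on therapy: 0.7 months after one cycle, 24.1 months after all 35 without delay. The larger totals require that patient to complete therapy and survive follow-up. They are not caps, because delays lengthen therapy and 24 to 30 is only an expectation.

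**5. What the shorter clock still gives.** Overall and progression-free survival run from registration (11.2.2). Two years after accrual may mean two years after each enrolment or two years after accrual closes. On either reading the last enrolee is followed to month 48 when N = 24, so every patient has at least 24 months of potential follow-up from registration.

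**6. What the primary analysis uses.** The rule is at least 6 responders among 20. The exact binomial probability of reaching it is 0.0673 at a true rate of 15% and 0.874 at 40%, agreeing with the stated 0.07 and 87%. Neither calculation contains accrual time or follow-up length. The readout moves from month 24 + 6 = 30 to month 30 + 6 = 36 if N = 30.

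**7. Which text controls conduct.** Enrolment closes on patient counts (13.2.1), not on a month. Survival contacts follow Section 5.6 and the calendar. The off-study list in Section 5.7 has no date. Section 14 is the publication plan: it uses the end of study to set reporting deadlines and does not tell sites to stop contacts.

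**The case for a change.** The strongest opposing argument is that a different starting point for follow-up is not rounding. About four years might stretch to 4.5, but not to the 6.0 to 6.5 years that Section 5.6 permits. Because the end of study is defined by alternatives, one pointing to Section 13.2, and footnote d uses that term, a sponsor could close the study at month 48 and cite the plan. The publication deadlines in Section 14 would shift as well. A few words would remove the doubt.

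The inconsistency stands, for overall survival in particular, since both clocks cover it. The consequence does not. It needs a reading that no section imposes and that conflicts with the explicit follow-up instruction in Section 5.6. Even then, an early calendar close would be administrative censoring determined by entry date. Kaplan-Meier estimation handles that; the cost is precision at late times, not bias, provided prognosis does not drift with entry date. Section 13.6 also reports follow-up by the reverse Kaplan-Meier method, so any shortening would be visible. Its size cannot be taken from the documents, because they give no expected treatment duration.

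**Conclusion.** No change to the plan follows. The 24 months and four years are correct sums on the lowest expected enrolment and the shorter clock, presented as anticipated and approximate. The discrepancy is 6 months of accrual and half a year of total duration at N = 30. On the Section 5.6 clock the total could reach about 72 to 78 months, but only if the last enrolee completes all 35 cycles undelayed and survives a further 24 months.

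The response rule, its error rate and its power are unaffected, and the time-to-event methods remain sound. An analyst would use the data cut actually made, censor as Section 11.2 directs and report the follow-up obtained. Restating the forecast would tidy the text without altering a result or a conclusion.

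This rests on two assumptions: that sites follow Section 5.6 for contacts, and that the four-year figure is read as a forecast and not as a closing date. The wording of Sections 5.6, 5.7 and 13.2.2 supports both.

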13.3 Stratification Factors

Response rates, PFS and DOR will also be reported for each histology (EBV+ DLBCL, PMBL, TCHRLCL).

13.4 Interim Monitoring Plan

The trial will be monitored by a DSMC and will be stopped at the judgment of the DSMC should excessive toxicity be observed. There are no stopping rules for futility.

13.5 Analysis of Primary Endpoints

Primary and secondary analyses will be performed on all patients who had measurable disease present at baseline, received at least one cycle of study drug, and had their disease re-evaluated for response. Response rates will be tabulated and reported as proportions with 90% exact binomial confidence intervals for each point estimate.

See Section 11 for additional details and definitions.

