d:	In subjects who discontinue therapy without documented disease progression every effort should be made to continue monitoring disease by radiographic imaging every 12 weeks (\pm 14 days) until one of the following occurs: start of new anti-cancer therapy; documented disease progression by investigator assessment; end of study; or death, whichever occurs first												
e:	After the start of new anti-cancer treatment or documented disease progression by investigator assessment, the subject will transition to the Survival Follow-up and the patient or their primary physician should be contacted by telephone or email every 12 weeks (+/- 14 days) to assess survival status												
f:	Patients who achieve a metabolic complete remission (defined as Deauville 1-3) may be followed subsequently with CT of the chest, abdomen, and pelvis rather than PET/CT at the discretion of the treating investigator; after cycle 9 radiology restaging will occur every 4 cycles (e.g. on cycles 13, 17, 21, etc) until cycle 33. There is a \pm 3-day window for radiology tests but radiographic restaging should occur prior to drug administration for a cycle on which restaging is due though this could include a scan the same day as but prior to dosing of study drug.												
g:	At screening, fresh biopsy (1 core) or archival tissue within 90 days of C1D1 (5 unstained slides, 5 μ m) is required, unless an exception is given by the study chair. Fresh biopsy samples at week 6 (\pm 7 days) and at the time of discontinuation due to disease progression are optional but highly recommended unless the tumors are considered inaccessible by the treating physician or concerns that a biopsy is contraindicated due to safety concerns.												
h:	In subjects with an unconfirmed PD assessment who continue study therapy a radiology assessment should be performed 12 weeks (\pm 7 days) from the time of unconfirmed PD assessment or at the time of treatment discontinuation. If a scan was previously obtained within 30 days of the time of treatment discontinuation then a repeat radiology examination is not required. Imaging should occur at any time that disease progression is suspected. Those who have EBV positive lymphoma will have EBV viral load assessed at screening. If positive, it will be subsequently checked at every disease assessment.												

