11. MEASUREMENT OF EFFECT

11.1 Response Criteria

The primary objective of this study is overall response rate (ORR). Response and progression will be evaluated following the 2014 Lugano criteria for the primary endpoint and LyRIC for secondary endpoint. Patients will undergo tumor restaging, using the appropriate combination of imaging and bone marrow biopsies, after cycles 2 and 5 and 8 and then every 4 cycles thereafter until cycle 32. Radiographic restaging will also be performed at the 60-day post-treatment follow-up visit and at pre-specified intervals thereafter (see Study Calendar, section 10). Imaging will consist of PET/CT scans until the patient has achieved a metabolic CR (defined as Deauville score 1-3) at which juncture transition to CT of the chest, abdomen and pelvis will be acceptable at the discretion of the treating physician. Response assessment will follow standard criteria (Lugano criteria) for lymphoma. Bone marrow biopsy will be required within 30 days of radiology testing to confirm CR for patients with marrow involvement at baseline. A repeat bone marrow biopsy is not necessary to confirm CR if there was no marrow involvement at baseline.

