13.6.1 Safety analyses

Safety evaluations will be performed for the total cohort of patients including all who received at least one dose of study treatment. Incidence, severity, and type of adverse events (AEs) will be tabulated and reported as proportions.

SAEs, deaths, and other safety-related events resulting in discontinuation from study will be reported separately.

Safety analyses may also be performed by sub-populations of patients depending on the size of each.

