13.7 Reporting and Exclusions

The primary analyses will be on an intent-to-treat basis, considering all patients who are enrolled on study. Secondary analyses and toxicity analyses will be performed on the subset of eligible patients who received at least 1 dose of study drug.

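### Sections 13.5, 13.6 and 13.7 name different analysis sets, and the set in 13.5 raises the reported response rate by leaving out patients who were never re-evaluated

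*Combined protocol and SAP*

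**What the plan says.** Section 13.5, the section headed for the primary endpoint, applies one set to both primary and secondary analyses: "all patients who had measurable disease present at baseline, received at least one cycle of study drug, and had their disease re-evaluated for response".

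Section 13.7 says otherwise on both. For the primary analysis: "The primary analyses will be on an intent-to-treat basis, considering all patients who are enrolled on study". For the rest: "Secondary analyses and toxicity analyses will be performed on the subset of eligible patients who received at least 1 dose of study drug".

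Section 13.6 has a third wording. Complete response rate, duration of response, duration of complete response, progression-free survival (PFS) and overall survival (OS) are to be reported for the whole cohort, without saying who belongs to it.

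The decision rule in section 13.2.2 is written on enrolment: "Assuming at least 20 patients are enrolled, we would consider the treatment promising if at least 6 patients respond". On safety, section 13.6.1 says: "Safety evaluations will be performed for the total cohort of patients including all who received at least one dose of study treatment". It has no eligibility condition, whereas 13.7 restricts toxicity to eligible patients.

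**The concern.** The primary endpoint is a single proportion, so its denominator must be fixed in advance and be unique. Here two current sections give two denominators, and neither is labelled as supportive. The trial is open-label, so the choice could be made after responses are known.

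The two denominators are not neutral alternatives. The set in 13.5 depends on something that happens after treatment starts, namely a disease re-evaluation. The first scheduled restaging comes after cycle 2 (section 11.1), about 6 weeks in. Treated patients who die, are lost or start other therapy before any scan would leave the analysis. The Study Calendar (section 10, footnote e) sends the last group to survival contact only: "After the start of new anti-cancer treatment or documented disease progression by investigator assessment, the subject will transition to the Survival Follow-up". All of these patients are treatment failures or unknowns; none can have a recorded response. At stake are the headline ORR and its 90% interval. If 13.5 were applied to PFS and OS, some of the earliest events would be lost as well.

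**Working it through.** **1. The sets side by side**

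| Analysis | 13.5 | 13.6 / 13.6.1 | 13.7 |
|---|---|---|---|
| Primary ORR | response-evaluable | not addressed | all enrolled (intent-to-treat) |
| Secondary efficacy | response-evaluable | whole cohort, undefined | eligible, at least 1 dose |
| Toxicity | not addressed | all with at least 1 dose | eligible, at least 1 dose |

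Each row with more than one entry is inconsistent, and no section ranks the entries.

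**2. The plan's own figures**

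Inputs from 13.2.2: n = 20 enrolled, success at 6 or more responses, null 15%, alternative 40%.

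- P(X ≥ 6 | 20, 0.15) = 0.0673; the plan states 0.07.
- P(X ≥ 6 | 20, 0.40) = 0.8744; the plan states about 87%.
- Widest exact 90% interval at n = 20 (10/20): 30.2% to 69.8%, half-width 19.8 points; the plan states about ±20%.

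The figures reproduce with 20 enrolled patients as the denominator, which agrees with 13.7.

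**3. Direction**

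Let x be the responders, N the number enrolled and m the number never re-evaluated, with d = m/N. The all-enrolled ORR is x/N, with unassessed patients as non-responders. The 13.5 ORR is x/(N − m). The ratio is N/(N − m) = 1/(1 − d): 1.05 at d = 5%, 1.11 at 10%, 1.25 at 20% (assumed values). The factor is exact for the point estimate; the interval limits also move up, but not in exact proportion.

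The re-evaluation clause does most of the work. Measurable disease is already an entry criterion (3.1.12), and registrations of untreated patients are cancelled (4.1, 4.3).

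**4. Size, with m assumed**

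Exact (Clopper-Pearson) 90% intervals, the method named in 13.5. N = 20 is the design number in 13.2.2, and N = 24 is the lower end of the 24–30 lymphoma patients expected in 13.2.1.

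| Enrolled | m dropped | ORR | 90% CI |
|---|---|---|---|
| 20 | 0 | 6/20 = 30.0% | 14.0–50.8 |
| 20 | 1 | 6/19 = 31.6% | 14.7–53.0 |
| 20 | 2 | 6/18 = 33.3% | 15.6–55.4 |
| 20 | 4 | 6/16 = 37.5% | 17.8–60.9 |
| 24 | 0 | 6/24 = 25.0% | 11.5–43.5 |
| 24 | 2 | 6/22 = 27.3% | 12.6–46.8 |
| 24 | 4 | 6/20 = 30.0% | 14.0–50.8 |

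Dropping two patients adds 3.3 points at N = 20 and 2.3 points at N = 24.

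**5. The decision rule**

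Dropping non-responders leaves x unchanged. With enrolment fixed at 20, 6 responders are still 6 responders, and the 0.0673 error rate stands.

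**6. PFS and OS**

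Section 11.2.2 starts both at registration and counts death from any cause. Requiring a later re-evaluation would remove patients who died before it.

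**The case against.** The strongest reply is that the intended set is clear enough. Both 13.2.2 and 13.7 speak of enrolled patients, and 13.6, the section specific to PFS and OS, points away from the 13.5 restriction. The protocol also works to keep patients assessable. Footnote h of the calendar says "Imaging should occur at any time that disease progression is suspected", section 11.1 adds "Radiographic restaging will also be performed at the 60-day post-treatment follow-up visit", and footnote d asks for continued imaging of patients who stop without progression. The excluded group is therefore smaller than all early failures, and may be very small.

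Most of that stands. It makes 13.7 the likelier intent for the primary set and limits the size of the effect. It does not remove the conflict: 13.5 is current text under the primary-endpoint heading, and 13.7 does not say how an unassessed patient is scored.

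A reader might infer three stronger things that the documents do not support.

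- *That the go/no-go decision is inflated.* At fixed enrolment the count does not change. If 20 evaluable patients were recruited instead, with an all-enrolled ORR of 15%, the chance of 6 or more responses would rise from 0.067 to 0.102 at d = 10% or 0.157 at d = 20% (assumed). But 13.2.2 counts enrolled patients, and nothing in the plan replaces unevaluable ones.
- *That 13.5 turns a failed result into one that excludes the 15% null.* The lower limit passes 15% for 6/18, but not for 6/22 (12.6%). The crossing depends on the inputs chosen, and the limit has no role in the count rule. A 90% interval has 5% in each tail and the rule has 6.7%, so 6/20 meets the rule even though its lower limit is 14.0%.
- *That PFS and OS are already biased.* They are biased only if the analyst applies 13.5 to them.

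**Conclusion.** The inconsistency is real and covers the primary, secondary and toxicity sets. If 13.5 is followed, the reported ORR is biased upward whenever there is at least one responder and at least one enrolled patient without a re-evaluation. The size is unknown. In the illustrations above, one to four unassessed patients out of 20 raise a 30.0% ORR by 1.6 to 7.5 points, and two to four out of 24 raise a 25.0% ORR by 2.3 to 5.0 points. These rest on assumed numbers of responders and unassessed patients; the documents give neither a non-evaluable rate nor an allowance for one. The success count and its stated error rates are unaffected at fixed enrolment. This should be fixed before analysis, but it does not undermine the design.

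**What to change.** - **13.5:** replace the whole population sentence; deleting only the re-evaluation clause would still leave it at odds with 13.7. State that the primary ORR uses all enrolled lymphoma patients on an intent-to-treat basis, and that patients without a post-baseline assessment count as non-responders. This deliberately narrows the all-enrolled wording of 13.7 to the population of objective 1.2. Histiocytic and dendritic cell patients are reported separately, as 1.3 and 13.2.1 already intend.
- **Sensitivity analysis:** keep the response-evaluable ORR, labelled as such.
- **13.6 and 13.7:** use one definition of the cohort for complete response rate, PFS and OS: all enrolled patients who received at least one dose, whether or not re-evaluated. Report duration of response in responders only.
- **13.7, toxicity:** remove the eligibility condition so that the set matches 13.6.1.

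The cost is wording in three sections, with no new data, visits or patients. The reported ORR may be slightly less favourable than under 13.5.
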